7.1.4.3 Target/Non-Target Lesions

All measurable lesions, up to a maximum of 2 per organ and 5 in total, should be identified as target lesions to be measured and recorded at baseline. The target lesions should be representative of all involved organs. Target lesions will be selected based on their size (the lesion with the longest diameter) and suitability for accurate repeated measurements. At baseline, a sum of the longest diameters for all target lesions will be calculated and recorded as the baseline tumor burden. The baseline sum will be used as the reference point to determine the objective tumor response of the target lesions.

Measurable lesions other than the target lesions and all sites of non-measurable disease will be identified as non-target lesions and will be recorded at baseline. Non-target lesions will be evaluated at the same time points as target lesions.

7.1.4.4 Response in Measurable Lesions (RECIST 1.1)

At baseline, the sum of the longest diameters (SumD) of all target lesions (up to 2 lesions per organ, up to total 5 lesions) is measured. At each subsequent tumor assessment, the SumD of the target lesions and of new, measurable lesions (≥ 10 ; up to 2 new lesions per organ, total 5 new lesions) are added together to provide the total measurable tumor burden (TMTB):

TMTB = SumD target lesions + SumD new, measurable lesions

Percentage changes in TMTB per assessment time point describe the size and growth kinetics of both old and new measurable lesions as they appear. At each tumor assessment, the response in target and new measurable lesions is defined based on the change in TMTB.

- Complete Response (CR): Disappearance of all target lesions. Any pathological lymph nodes (whether target or non-target) must have reduction in short axis to < 10 mm.
- Partial Response (PR): At least a 30% decrease in the sum of diameters of target lesions, taking as reference the baseline sum diameters.
- Progressive Disease (PD): At least a 20% increase in the sum of diameters of target lesions, taking as reference the smallest sum on study (this includes the baseline sum if that is the smallest on study). In addition to the relative increase of 20%, the sum must also demonstrate an absolute increase of at least 5 mm. (Note: the appearance of one or more new lesions is also considered progression).
- Stable Disease (SD): Neither sufficient shrinkage to qualify for PR nor sufficient increase to qualify for PD, taking as reference the smallest sum diameters while on study.

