3.2 Secondary Objectives

Objective: To evaluate efficacy as measured by the overall response rate and rate of 6 month PFS in subjects with persistent/recurrent, loco-regional or metastatic SCCA of the anorectal as determined by irRECIST

Objective: To evaluate the safety and tolerability of ADXS11-001 in subjects with persistent/recurrent, loco-regional or metastatic SCCA of the anorectal canal by NCI CTCAE 4.0.

Objective: To evaluate the additional parameters of efficacy (duration of response, PFS and overall survival) of ADXS11-001 in subjects with persistent/recurrent, loco-regional or metastatic SCCA of the anorectal canal as determined by RECIST 1.1 and irRECIST.

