7.1.4.5 Immune-Related Response in Measurable Lesions (irRECIST)

In addition to evaluation using RECIST 1.1 criteria, an immune response adaptation of RECIST will be applied to this trial. The essential differences between irRECIST and RECIST criteria are as follows:

- New measurable lesions do not necessarily constitute progressive disease and they should be added into the total tumor burden. New non-measurable lesions do not constitute disease progression but will prevent the determination of an irCR.

- Apparent disease progression should be confirmed after 4 weeks in the absence of symptoms consistent with clinical deterioration.

At baseline, the sum of the longest diameters (SumD) of all target lesions (2 per organ and 5 in total) is measured. At each subsequent tumor assessment, the SumD of the target lesions and of new, measurable lesions (≥ 10 mm [lymph nodes ≥ 15 mm in shortest diameter]; up to 2 new lesions per organ, total 5 new lesions) are added together to provide the total measurable tumor burden (TMTB):

$TMTB = \text{SumD target lesions} + \text{SumD new, measurable lesions}$

Percentage changes in TMTB per assessment time point describe the size and growth kinetics of both old and new measurable lesions as they appear. At each tumor assessment, the response in target and new measurable lesions is defined based on the change in TMTB (after ruling out irPD) as follows:

Complete Response (irCR): complete disappearance of all target and new, measurable lesions, with the exceptions of lymph nodes which must decrease to < 10 mm in short axis

Partial Response (irPR): decrease in TMTB $\geq 30\%$ relative to baseline (see below)

Stable Disease (irSD): not meeting criteria for irCR or irPR, in absence of irPD

Progressive Disease (irPD): increase in TMTB $\geq 20\%$ relative to nadir

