7.1.4.8 Overall Response

Overall response will be determined based on RECIST 1.1 criteria and by irRECIST criteria (Table 9). Overall response according to irRECIST is derived from the responses in measurable lesions (based on TMTB) and the presence of any non-measurable lesions.

Table 9 Tumor Response Evaluation: Comparison of RECIST 1.1 and irRECIST

Criteria	RECIST1.1	irRECIST
New measurable lesions (≥ 10 mm)	Always represents PD	Incorporated into tumor burden

Criteria	RECIST1.1	irRECIST
New non-measurable lesions (< 10 mm)	Always represents PD	Does not define progression but precludes irCR
Non-Target lesions	Changes contribute to defining BOR of CR, PR, SD, and PD	Contribute to defining irCR (complete disappearance required)
CR	Disappearance of all lesions	Disappearance of all lesions
PR	≥ 30% decrease in the sum of the longest diameter of all target lesions compared with baseline, in absence of new lesions or unequivocal progression of non-target lesions	≥ 30% decrease in tumor burden compared with baseline
SD	Neither sufficient shrinkage to qualify for PR nor sufficient increase to qualify for PD, taking as reference the smallest sum diameters while on study	Neither a 30% decrease in tumor burden compared with baseline nor a 20% increase compared with nadir can be established
PD	At least 20% increase in sum of diameters of target lesions, taking as reference the smallest sum on study. In addition to the relative increase of 20%, the sum must also demonstrate an absolute increase of at least 5mm. The appearance of one or more new lesions is also considered progression.	At least 20% increase in tumor burden compared with nadir (at any single time point) ^a

irRECIST = immune-related Response Evaluation Criteria in Solid Tumors; BOR = best overall response; CR = complete response; irCR = immune-related complete response; PD = progressive disease; PR = partial response; SD = stable disease;

^a Patients with an initial finding of progressive disease (irPD) before or at the 8-week imaging assessment, but without rapid clinical deterioration, require confirmation of irPD with a second, consecutive scan obtained ≥ 4 weeks from the initiation documentation. Patients will continue to receive study treatment until irPD is confirmed at this later time point. Best overall response (BOR) will therefore include responses occurring at any time before disease progression and after early progression (i.e., within the first 9 weeks of the study).

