7.1.4.8.1 Best Overall Response (RECIST 1.1)

The best overall response is the best response recorded from the start of the study treatment until the end of treatment taking into account any requirement for confirmation. The patient's best overall response assignment will depend on the findings of both target and non-target disease and will also take into consideration the appearance of new lesions (Table 10).

Table 10 Best Overall Response (RECIST 1.1)

Target Lesions	Non-Target Lesions		Overall Response
	Baseline Lesions	Unequivocal New Lesions	
Baseline (Index) and New Measurable Lesions	CR	No	CR

Target Lesions Baseline (Index) and New Measurable Lesions	Non-Target Lesions		Overall Response
	Baseline Lesions	Unequivocal New Lesions	
CR	Non-CR/Non-PD	No	PR
CR	NE	No	PR
PR	Non-PD or NE	No	PR
SD	Non-PD or NE	No	SD
Not all evaluated	Non-PD	No	NE
PD	Any	Yes or No	PD
Any	PD	Yes or No	PD
Any	Any	Yes	PD

CR = complete response; NE = not evaluable at a particular time point; PR = partial response; SD = stable disease; PD = progressive disease

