7.1.4.8.2 Immune-Related Best Overall Response (irRECIST)

The immune-related best overall response (irBOR) is the best irRC overall response over the study as a whole, recorded between the date of first dose until the last tumor assessment prior to subsequent therapy (including tumor resection surgery) for the individual subject in the study (Table 11). As with the primary definitions of tumor response, early progression (i.e., irPD occurring prior to Week 8) will not preclude an irBOR of irCR, irPR or irSD resulting from the Week 8 assessment. An assessment of irPD at or after Week 8 will preclude a subsequent irBOR of irCR, irPR or irSD. However, any post-progression clinical activity in subjects with irBOR of irPD may be summarized for exploratory purposes.

Table 11 Immune-Related Best Overall Response (irBOR)

Target Lesions Baseline (Index) and New Measurable Lesions	Non-Target Lesions ^a		irRC Overall Response
	Total Measurable Tumor Burden	Baseline Lesions	
irCR	irCR	No	irCR
irCR	irSD	No	irPR
irPR	irCR or irSD	No	irPR
irSD	irCR or irSD	No	irSD

Target Lesions Baseline (Index) and New Measurable Lesions	Non-Target Lesions ^a		irRC Overall Response
	Total Measurable Tumor Burden	Baseline Lesions	
irPD	Any	Yes or No	irPD
Any	Unequivocal Progression	Yes or No	irPD
Any	Any	Yes	irPD

irCR = immune-related complete response; irPR = immune-related partial response; irSD = immune-related stable disease; irPD = immune-related progressive disease

^a Any increase in the size or number of non-measurable lesions does not necessarily imply an overall response of irPD. If these lesions become measurable (≥ 10 mm) at a subsequent assessment, their measurement will at that point start to contribute to the total measurable tumor burden. To achieve unequivocal progression of non-target lesions, there must be substantial worsening in non-target disease that is of a magnitude that the Investigator feels it is important to change therapy. Equivocal findings of progression of non-target lesions (e.g., small and uncertain new lesions; cystic changes or necrosis in existing lesions) should be considered irSD, and treatment may continue until the next assessment.

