8.3 Analysis of Study Endpoints

8.3.1 Analysis of Primary Endpoints for Efficacy

The following are the primary efficacy endpoints for both phases;

1. Overall Tumor Response (measured by RECIST 1.1);
2. Progression-Free Survival (PFS)

These endpoints are well established and commonly used to evaluate signs of clinical activity and efficacy.

The overall tumor response rates will be tabulated for all patients by treatment stage. PFS is defined as the time from treatment start until disease progression or death whichever occurred earlier. Patients who have not progressed or who are still alive at the time of evaluation will be censored for the analysis.

KM method will be used for estimating median times for PFS. The 95% confidence intervals of the medians will be presented.

Subject disposition, demographic and baseline subject characteristics will be summarized separately for Stage 1 and Stage 2. AEs will be classified and summarized by type, incidence, severity, and causality. All AEs will be summarized by subject, treatment, and disease. All subjects who receive at least 1 dose of ADXS11-001 will be included in the safety analyses.

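### The RECIST 1.1 rules for the primary endpoints contradict themselves on new lesions and leave best response open after progression, so the same scans can be scored two ways

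*Combined protocol and SAP*

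**What the plan says.** Section 8.3.1 names as a primary endpoint "Overall Tumor Response (measured by RECIST 1.1"), together with PFS. Section 3.1 ties both the response rate and the 6-month PFS rate to RECIST 1.1. The irRECIST versions are listed under "3.2 Secondary Objectives".

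On new lesions under RECIST 1.1, Section 7.1.4.4 opens by adding new measurable lesions to the target sum to form TMTB, and states: "At each tumor assessment, the response in target and new measurable lesions is defined based on the change in TMTB". The bullets that follow define PR and PD on target lesions only, with a note that a new lesion is progression. For both measurable and non-measurable new lesions, the RECIST 1.1 column of Table 9 reads "Always represents PD". Section 7.1.4.5 presents the additive rule as an essential difference of irRECIST from RECIST: "New measurable lesions do not necessarily constitute progressive disease and they should be added into the total tumor burden".

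On the response window, Section 7.1.4.8.1 (RECIST 1.1) says: "The best overall response is the best response recorded from the start of the study treatment until the end of treatment", subject to any confirmation requirement. Section 5.10 allows treatment to continue after radiologic progression under stated conditions.

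On the irRECIST side, Section 7.1.4.8.2 says: "An assessment of irPD at or after Week 8 will preclude a subsequent irBOR of irCR, irPR or irSD". Footnote a of Table 9 deals with "Patients with an initial finding of progressive disease (irPD) before or at the 8-week imaging assessment" and lets best response include responses after such early progression.

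**The concern.** A single-arm trial whose primary endpoints are a response rate and a 6-month PFS rate needs one rule that turns a set of scans into a category. For RECIST 1.1 there are two, within one section. A programmer or site following the opening paragraph of Section 7.1.4.4 would apply irRECIST under the RECIST 1.1 name; one following the bullets would not.

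The response window is a second, independent gap. Treatment may run past progression and best response is collected to the end of treatment, so a later shrinkage could be entered as a RECIST 1.1 response after RECIST 1.1 progression has been recorded. The irRECIST section does limit responses after progression; the RECIST 1.1 section does not.

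At stake are the Stage 1 decision, the final response rate and, for the new-lesion rule, the 6-month PFS rate. It would also become unclear whether the primary and secondary analyses differ in the way their names imply.

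**Working it through.** **1. What happens to a new measurable lesion under RECIST 1.1**

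| Place | Rule |
|---|---|
| 7.1.4.4, opening text | Added to the target sum; response follows the change in TMTB |
| 7.1.4.4, bullets | PR and PD on target lesions only; a new lesion is PD |
| 7.1.4.6, PD note | PD |
| Table 9 | Always PD; the PR row requires that no new lesion is present |
| Table 10 | Last row: an unequivocal new lesion gives PD; but the target column is headed as including new measurable lesions |

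The opening text of 7.1.4.4 and the heading in Table 10 stand against everything else.

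**2. Effect on response.** Illustrative values: baseline target sum 100 mm; follow-up targets 55 mm; one new lesion of 12 mm.

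- TMTB = 55 + 12 = 67 mm.
- Change = (67 - 100)/100 = -33%.
- TMTB sentence: at least a 30% decrease, so PR.
- Note in the same section: PD.

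**3. Effect on PFS.** Smallest sum 100 mm; targets 80 mm; new lesion 12 mm. TMTB = 92 mm, a change of -8%: stable by the TMTB sentence and no PFS event, but PD by the note. The error can go only one way. Without a new lesion, TMTB equals the target sum; with one, the note already gives the worst category. The TMTB reading can only raise response and PFS.

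**4. Best-response window.** Take a 100 mm baseline and the protocol's own thresholds. A scan at 100 x 1.20 = 120 mm is PD (+20%, and +20 mm exceeds the 5 mm minimum). A later scan at 100 x 0.70 = 70 mm meets PR against baseline. Section 5.10 foresees a repeat scan judged against baseline, and treatment may continue. Nothing in Section 7.1.4.8.1 says that the 70 mm scan no longer counts. PFS is unaffected, because its event is the first progression.

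**5. Size.** The stage sizes, 31 + 24 = 55, are not in dispute.

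- One subject: 1/31 = 3.2 points in Stage 1; 1/55 = 1.8 points overall.
- Response arm of the gate: Section 8.2 gives a count of 3 or more, and also a rate of at least 10%. 3/31 = 9.7% and 4/31 = 12.9%, so these two statements already differ by one subject.
- PFS arm, at least 20%: 6/31 = 19.4% and 7/31 = 22.6%, so 7 subjects if read as a simple proportion.

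Sensitivity of the response arm alone: X ~ Binomial(31, q + m), where q is the true response rate and m the share of all subjects counted as PR instead of PD. The documents give no value for m; the values below are assumptions.

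| q | m | P(X >= 3) | P(X >= 4) |
|---|---|---|---|
| 5% | 0 | 0.201 | 0.067 |
| 5% | 2% | 0.371 | 0.169 |
| 5% | 3% | 0.456 | 0.233 |
| 5% | 5% | 0.611 | 0.376 |
| 10% | 0 | 0.611 | 0.376 |
| 10% | 2% | 0.736 | 0.520 |
| 10% | 3% | 0.786 | 0.586 |
| 10% | 5% | 0.864 | 0.704 |

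**6. irRECIST (secondary endpoints only)**

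- *New non-measurable lesions.* Sections 7.1.4.5 and 7.1.4.7 and Table 9 say that they are not progression in themselves and only rule out irCR. Table 11's last row gives irPD whenever its third column is 'Yes', and its irPR and irSD rows all require 'No'. That column's heading did not survive in the text read here; its counterpart in Table 10 is headed as unequivocal new lesions.
- *irPD at Week 8.* The first on-treatment scan is due at Week 8 (plus or minus 1 week). Footnote a of Table 9 covers progression before or at that scan and allows a later response to count. Section 7.1.4.8.2 allows this only for progression before Week 8. Progression found at Week 8 itself falls under both rules.

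**The case against.** The best defence is that the intended RECIST 1.1 rule is easy to see. The bullets in Section 7.1.4.4, the note in Section 7.1.4.6 and the body of Tables 9 and 10 all make a new lesion PD, and Section 12.3 says that RECIST 1.1 will be used. The TMTB paragraph looks copied from Section 7.1.4.5. This stands in part. A reader might infer that the primary response rate is misclassified, and the documents do not support that. They show that it can be classified two ways, with most of the text favouring one of them.

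On the window, Section 7.1.4.8.1 does refer to confirmation and to new lesions through Table 10. But confirmation is not a cut-off at progression, and Table 10 does not say how a PD by target growth bears on a later PR. That gap stays open, although it needs both treatment past progression and a later response.

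A reader might also infer that the irRECIST tables distort the primary response rate. They cannot: they govern secondary objectives. The Table 11 conflict is clear only for new non-measurable lesions, because new measurable ones already enter its first column through TMTB.

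Finally, a reader might infer that one subject settles Stage 1 at 3 versus 4 responses. The protocol also states a count of 3 or more, and the gate opens on PFS alone. One response is decisive only when the PFS arm is not met.

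**Conclusion.** The point holds as an ambiguity in the primary endpoint definitions. Section 7.1.4.4 contains an irRECIST rule that contradicts its own bullets, and RECIST 1.1 best response has no stated end at progression. Response is exposed to both problems, 6-month PFS only to the first. Each reclassified subject is worth 3.2 points in Stage 1 and 1.8 points over 55 subjects. Both problems favour the drug.

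How many subjects would be affected cannot be read from the documents. If 2% to 5% of subjects were counted as PR instead of PD at a true rate of 10%, the chance of at least 3 of 31 would rise from 0.611 to between 0.736 and 0.864, and of at least 4 of 31 from 0.376 to between 0.520 and 0.704. These figures ignore the PFS arm.

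The primary definitions must be corrected before response data are read. The two irRECIST conflicts are real but of lower severity. The documents give no basis for saying how often progression at the first scan is later reversed, so no size is put on the Week 8 conflict. Section 8.1 defers analysis detail to a SAP; the text available contains no rule that settles these points, and the protocol would need aligning even if one exists.

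**What to change.** Primary endpoints:

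1. Delete the TMTB text from Section 7.1.4.4, leaving the target-lesion bullets and the note that a new lesion is PD.
2. Remove new measurable lesions from the heading of Table 10's target column.
3. State in Section 7.1.4.8.1 that RECIST 1.1 best overall response counts only assessments up to first RECIST 1.1 PD.

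Secondary endpoints, lower priority:

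4. In Table 11, drop the last row and let the irPR and irSD rows accept 'Yes or No', so that a new non-measurable lesion precludes irCR only. Dropping the row alone would leave such a subject with irPR or irSD without an applicable row. The combination irCR, irCR and 'Yes' also needs a row: the text rules out irCR, and the irPR definition (TMTB down at least 30%) is met.
5. Give irPD at the Week 8 scan one best-response rule, stated identically in footnote a of Table 9 and in Section 7.1.4.8.2.

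The cost is text, two tables and derivation code. No extra scans are needed, and the treatment provisions in Section 5.10 are not touched. The downside is that some post-progression responses no longer count in the primary endpoint; they can still be described separately as exploratory.

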7.1.4.5 Immune-Related Response in Measurable Lesions (irRECIST)

In addition to evaluation using RECIST 1.1 criteria, an immune response adaptation of RECIST will be applied to this trial. The essential differences between irRECIST and RECIST criteria are as follows:

- New measurable lesions do not necessarily constitute progressive disease and they should be added into the total tumor burden. New non-measurable lesions do not constitute disease progression but will prevent the determination of an irCR.

- Apparent disease progression should be confirmed after 4 weeks in the absence of symptoms consistent with clinical deterioration.

At baseline, the sum of the longest diameters (SumD) of all target lesions (2 per organ and 5 in total) is measured. At each subsequent tumor assessment, the SumD of the target lesions and of new, measurable lesions (≥ 10 mm [lymph nodes ≥ 15 mm in shortest diameter]; up to 2 new lesions per organ, total 5 new lesions) are added together to provide the total measurable tumor burden (TMTB):

$TMTB = \text{SumD target lesions} + \text{SumD new, measurable lesions}$

Percentage changes in TMTB per assessment time point describe the size and growth kinetics of both old and new measurable lesions as they appear. At each tumor assessment, the response in target and new measurable lesions is defined based on the change in TMTB (after ruling out irPD) as follows:

Complete Response (irCR): complete disappearance of all target and new, measurable lesions, with the exceptions of lymph nodes which must decrease to < 10 mm in short axis

Partial Response (irPR): decrease in TMTB $\geq 30\%$ relative to baseline (see below)

Stable Disease (irSD): not meeting criteria for irCR or irPR, in absence of irPD

Progressive Disease (irPD): increase in TMTB $\geq 20\%$ relative to nadir

